- The open-loop system will be set to recognize sensor glucose values <75 mg/dl, triggering an alert to the physician, who will deliver a bolus of 150 or 300 µg of glucagon via the pump, with the goal of preventing further decline in glucose values. Time will be reset to 0 at the time of glucagon delivery.
- Plasma glucose will be measured (YSI) at 5, 10, 20, 30, 45, 60, 90, and 120 minutes after glucagon administration to ensure successful treatment and glucose stability, and glucagon levels will be analyzed concurrently to determine magnitude of increase above baseline.
- If the open-loop algorithm issues a predictive alert or detects a sensor glucose level under 75 mg/dl within 30-120 minutes after the first dose of glucagon, a second dose of glucagon (either 150 micrograms if a predicted hypoglycemia alert, or 300 micrograms if sensor glucose is under 75 mg/dl) will be administered. If a second dose of glucagon is given, glucose levels will be monitored every 15 minutes for an additional 60 minutes.
- At time of alarm trigger and before each administration of glucagon, the Edinburgh Hypoglycemia Symptoms Score will be

assessed. This will be repeated at 15, 30 and 60 minutes following glucagon infusion.

- Thirty minutes after the last glucagon treatment, the OmniPod® pump will be removed, and lunch will be provided.
- Venous blood glucose will be monitored every 15 minutes for at least 2 hours to ensure stability prior to discharge from the clinical research unit. Prior to discharge, the pump insertion site will be examined, and sensors will be removed. Patient will be given a snack on discharge.
- Sensors will be downloaded for subsequent analysis of appropriateness of alert timing and trigger for glucagon bolus delivery.
- Blood samples collected during this visit will be processed and stored at -80 until analysis for insulin and incretin hormone levels (to verify typical patterns in response to meal ingestion), for baseline levels of cortisol, and for glucagon, to assess endogenous responses as well as post-bolus plasma levels.

Follow-Up Phone Call (1 to 3 days following Visit 3)

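### After one glucagon dose, pump removal and lunch at 30 minutes cannot be squared with a pump-delivered second dose possible until 120 minutes, and no glucose outcome has a lunch cut-off

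*Protocol*

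**What the plan says.** All the timing statements stand in the Protocol, Brief outline of treatments, Visit Day 3.

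- **Route.** On an alert the physician gives a bolus "of glucagon via the pump, with the goal of preventing further decline in glucose values".
- **Second dose.** If the algorithm predicts hypoglycemia or the sensor reads under 75 mg/dl "within 30-120 minutes after the first dose of glucagon, a second dose of glucagon" is to be given. Study duration allows at most two infusions.
- **Removal and lunch.** "Thirty minutes after the last glucagon treatment, the OmniPod® pump will be removed, and lunch will be provided".
- **Sampling after a dose.** The clock is set back to zero when glucagon is delivered; this sentence belongs to the first-alert step. "Plasma glucose will be measured (YSI) at 5, 10, 20, 30, 45, 60, 90, and 120 minutes after glucagon administration", and "glucagon levels will be analyzed concurrently to determine magnitude of increase above baseline". On the symptom score: "This will be repeated at 15, 30 and 60 minutes following glucagon infusion".
- **Sampling after a second dose.** "If a second dose of glucagon is given, glucose levels will be monitored every 15 minutes for an additional 60 minutes".
- **Before discharge.** "Venous blood glucose will be monitored every 15 minutes for at least 2 hours to ensure stability prior to discharge". The sensors stay in place until discharge and are then downloaded.

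On outcomes, Protocol Objectives lists glucose below 60, glucose above 180 and minutes in 60-180 mg/dl as secondary. SAP Study endpoints lists time below 75, plasma glucose below 60, and plasma glucose above 180 following glucagon, also as secondary. Neither section, nor the Protocol's Biostatistical Considerations, nor SAP Statistics, gives an end to these windows or a rule for values taken after lunch.

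**The concern.** The removal rule depends on which dose is the last, and the plan does not say when that is judged. For someone who has had one dose, the written removal time is the minute at which the second-dose window opens. Acting then makes the second-dose step impossible to carry out through the pump. Holding back means the 30-minute instruction is not followed.

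The choice also decides what the later samples measure. This is a study of post-prandial hypoglycemia, and lunch is a new meal. Glucose after lunch may rise because of the meal, or may begin a new post-prandial fall. Without a lunch cut-off, a value above 180 could be scored as rebound from glucagon, and an in-range value as protection by glucagon. Outcomes counted in minutes also depend on how long each person was observed. The SAP reports seven people enrolled, so one misattributed event, counted per person, is 1/7, or about 14%.

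**Working it through.** The plan gives no figure to reproduce; the check places its own times on one clock.

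**Inputs (Protocol, Visit Day 3).** Glucose series S = {5, 10, 20, 30, 45, 60, 90, 120} minutes after glucagon, with glucagon levels taken concurrently. Symptom scores at {15, 30, 60}. Second-dose window 30 to 120 minutes after dose 1. Lunch and removal at L = time of last dose + 30. A sample due at the lunch minute is counted as before lunch.

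**One dose, act at minute 30 (L = 30).**
- Second-dose window with the pump in place: 30 − 30 = 0 of 120 − 30 = 90 minutes.
- Glucose samples after lunch: {45, 60, 90, 120} = 4 of 8, and the same 4 glucagon levels.
- Follow-up after lunch: (120 − 30)/120 = 90/120 = 75%.
- Symptom scores after lunch: {60} = 1 of 3.

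**One dose, wait until the window closes (L = 120).**
- Glucose samples after lunch: 0 of 8.
- Delay against the written time: 120 − 30 = 90 minutes.

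**Two doses, dose 2 at t2 between 30 and 120.** L = t2 + 30, so lunch is 60 to 150 minutes after dose 1. The counts depend on how the sampling text is read.

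| Reading of the sampling text | Samples after lunch |
|---|---|
| Four added samples counted from dose 2: t2 + {15, 30, 45, 60} | 2 of 4, for every t2 |
| Four added samples placed after minute 120: {135, 150, 165, 180} | 4 if t2 < 105; 3 if 105 ≤ t2 < 120; 2 if t2 = 120 |
| Clock reset restarts the 8-sample series at dose 2: t2 + S | 4 of 8, for every t2 |
| First series continues on the dose 1 clock | 2 if 30 ≤ t2 < 60; 1 if 60 ≤ t2 < 90; 0 if t2 ≥ 90 |

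The reset sentence sits in the first-alert step, so whether it applies to dose 2 is unclear. The last two rows are therefore alternatives, and neither can be taken as the plan's intention.

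**Outcome windows.** The SAP's above-180 outcome starts at glucagon delivery and has no end. The below-60, below-75 and 60-180 outcomes have no stated end either. Whether the post-lunch samples counted above enter these outcomes is thus undecided. The documents give no data on the meal's effect, so its size cannot be calculated.

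**The case against.** The strongest reply is that the two instructions need not collide. The second dose is conditional. If the trigger comes at minute 30, dose 2 is given and dose 1 is no longer the last. If no trigger ever comes, removal at 30 minutes has breached nothing. The window closes at 120 minutes and infusions are capped at two, so the last dose can be identified at dose 2 or when the window closes. This stands in part: the conflict is prospective, arising because staff at minute 30 cannot see ahead. It does not remove the problem, since waiting for certainty rules out the written 30-minute timing for every one-dose participant.

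A reader might infer that the Protocol always takes the pump off as the window opens. The text does not support that: it holds only after a single dose and only if staff act at 30 minutes. A reader might also infer that the first sampling series certainly runs on past dose 2. The clock-reset sentence leaves that open.

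It can fairly be said that the pre-discharge series has its own stated purpose of checking stability, which suggests safety monitoring. That is reasonable, but it does not settle the status of the 45 to 120 minute samples.

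Finally, the affected glucose outcomes are secondary, in a small study with no power calculation. That limits the weight of the point.

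**Conclusion.** The point holds for a participant who has had one dose. The removal and lunch time and the second-dose window cannot both be honoured on the information available at minute 30. Depending on how the last dose is judged, either 4 of 8 glucose samples (75% of the two-hour follow-up) come after lunch, or none do and lunch is 90 minutes later than written. After two doses, lunch falls 60 to 150 minutes after dose 1, and the share of samples after it depends on an unclear clock reset.

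The secondary glucose outcomes have no lunch cut-off in the available text, so meal effects may be credited to or blamed on glucagon. It would go too far to say that the results are biased. The documents neither require nor exclude scoring post-lunch values, and they give nothing from which to size an effect. Nor is the Protocol's primary endpoint, detection and timing of the dose, affected for the first alert.

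The counts assume that sampling follows the written schedule and that lunch is given exactly 30 minutes after the dose treated as last. The statement about missing cut-offs covers only the text available, since part of the SAP file was removed before review. The point should be fixed, but it does not undermine the study.

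**What to change.** **Protocol.** The sponsor must reconcile the statements on removal and lunch, the second dose, the clock reset and sampling. Which timing governs is the sponsor's decision.

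**SAP.**
1. State the start and end of each glucose outcome window.
2. Report the post-glucagon glucose outcomes, the concurrent glucagon levels and the symptom scores twice: up to the recorded lunch time, and over the full scheduled sampling.
3. Add one participant-level listing giving the length of the observed window and each value below 60 or above 180, timed from dose and from lunch.
4. If lunch time was not recorded, say so.

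**Cost.** A few lines of text and one listing; no new samples. The SAP describes enrolment in the past tense, so if visits are complete only the reporting changes apply.

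**Downside.** The pre-lunch window may be as short as 30 minutes, its length depends on response, and it can miss a later rebound. The full-schedule view keeps those samples but mixes meal and glucagon effects. That is why both are shown.

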Study design:	
As a first step to developing new glucagon infusion delivery strategies for hypoglycemia, development of computer algorithms to predict timing and severity of hypoglycemia onset has been initiated, in collaboration with computational scientists at Harvard University School of Engineering. We have analyzed data collected from clinically-indicated diagnostic continuous glucose monitoring systems (iPRO CGMS) obtained from patients enrolled in the hypoglycemia clinic at the Joslin Diabetes Center. Extracted data, including continuous glucose monitoring sensor glucose values, age, gender, and body mass index, and food and activity logs, were used to develop computational algorithms to allow prediction of hypoglycemia.
 
This will be a Phase 2a, single-center, open-label, proof-of-concept study designed to test the ability of the control algorithm to detect and direct timing of G-Pump™ glucagon infused from an OmniPod® pump to prevent hypoglycemia in patients with post-bariatric hypoglycemia syndrome. While the algorithm will provide an alert as to when glucagon

	should be dosed to prevent hypoglycemia, there will be no automation in this clinical trial and it will ultimately be up to the physician to initiate dosing via the OmniPod® controller.
Study location:	Joslin Diabetes Center, Boston, MA USA.
Study duration:	The total length of the study will be approximately one week per patient, and involve up to two infusions of G-Pump™ glucagon at a single visit. The total time for enrollment and treatment will be approximately 3 months.
Sample size:	For this proof-of-concept study, success will be defined as meeting the primary endpoint in 3 of 5 participants. If this is not achieved, the algorithm will be revised, and an additional 5 participants may be recruited for additional study.
Subjects:	Adult male or female patients with post-bariatric hypoglycemia syndrome
Inclusion Criteria:	
1. Males or females diagnosed with ongoing post-bariatric hypoglycemia with prior episodes of neuroglycopenia, unresponsive to dietary intervention (low glycemic index, controlled carbohydrate portions) and trial of acarbose therapy at the maximally tolerated dose.2. Age 18-65 years of age, inclusive, at screening.3. Willingness to provide informed consent and follow all study procedures, including attending all scheduled visits.

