Brief outline of treatments:	
Methods:
 
Visit Day 1 - Screening:
 
• Adult male or female patients with PBH will be recruited from the hypoglycemia clinic at Joslin.• Patients will undergo a history and physical examination, with particular emphasis on inclusion and exclusion criteria.• Blood and urine samples will be obtained for screening laboratory testing including hemoglobin A1c, CBC, comprehensive chemistry, urinalysis, and pregnancy test (if applicable).• Consent forms will be reviewed in detail with potential participants. 
Visit Day 2 - CGM Sensor Placement:
 
• Two continuous glucose monitor sensors (Dexcom® G4 Platinum) will be placed on the anterior abdominal wall (to ensure sensor availability and calibration for visit day 3). Participants will be provided a glucometer and instructed in both sensor insertion and calibration techniques.• If patient has prior experience with sensor insertion and calibration
------------------------------	--

then this visit may occur concurrent with visit 1.

Visit Day 3 – Mixed Meal Testing (</= 3 days following Visit 2):

- Subjects will arrive in the morning after an overnight fast.
- An intravenous line will be inserted for blood sampling and to provide intravenous access. Placement of the Dexcom sensor will be verified, and calibration verified using at least 2 venous blood glucose samples obtained 15 minutes apart.
- An OmniPod® containing G-Pump™ glucagon will be inserted.
- Two blood samples will be obtained for measurement of plasma glucose (via YSI analytical device) immediately and for subsequent hormonal assays.
- The subject will then be asked to drink a liquid mixed meal containing 60 g of carbohydrates, e.g. Boost® Nutritional Drink, over 10 minutes.
- Blood samples will be collected for immediate (in room) glucose measurements (YSI) every 10 minutes, and hormonal profiles at 10, 20, 30, 60, 90, 120, 150, and 180 minutes. Once venous glucose levels fall below 90 mg/dl, glucose will be measured at 5 minute intervals (YSI). This blood sampling series will conclude once sensor glucose levels fall to <75 mg/dl. (See below for subsequent sample timing after clock is reset when glucagon is delivered.)

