Biostatistical Considerations:	
All subjects who have received at least one dose of glucagon will be included in the data analysis set. Adverse events, vital signs, physical examination, laboratory safety variables (Screening to Final Visit), EKG (Screening to Final Visit), and local tolerability data will be reviewed and summarized on an ongoing basis during the study to evaluate the safety of subjects. Safety data will be presented in tabular and/or graphical format and summarized descriptively, where appropriate.
 
Sensor and glucagon delivery request will be collected and evaluated for specificity and response time.
 
Glucagon, insulin, and incretin plasma concentration profiles will be analyzed with commercially available analytical methods and examined using repeated-measures ANOVA.
 
Success will be defined as meeting the primary endpoint in 3 of 5 participants. If this is not achieved, the algorithm will be revised, and an additional 5 participants may be recruited for additional study.

--------------------------------	---

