**NCT02733588**

**Document Date: February 13, 2017**

## Statistical Analysis Plan for Protocol XSGO-PB01

**Analysis Population.** Participants with a history of RYGB surgery and PBH with neuroglycopenia, uncontrolled on medical nutrition therapy and medications, were recruited from the hypoglycemia clinic. Exclusion criteria included fasting hypoglycemia, known insulinoma, major systemic illness, pregnancy, substance or alcohol abuse, recent steroid or investigational drug exposure, and use of medications (beyond hypoglycemia treatment) known to affect insulin secretion or action. The Joslin Diabetes Center Committee on Human Studies approved the study. Written informed consent was obtained from all participants. Six females and one male were enrolled. Two participants enrolled twice, in different stages of system development. All enrolled participants were included in the analysis.

**Study endpoints.** This iterative development clinical study was designed to evaluate the primary endpoints of safety and feasibility of the proposed system to predict and prevent severe hypoglycemia in patients with PBH. Secondary outcomes included prediction of imminent hypoglycemia by the automatic monitoring algorithm, minimization of time below a prespecified threshold (<75 mg/dL) using glucagon delivery, prevention of severe postprandial hypoglycemia (plasma glucose <60 mg/dL), and prevention of rebound hyperglycemia (plasma glucose >180 mg/dL) after glucagon delivery.

**Statistics.** As an algorithm iterative development study, sample size was not determined by a power calculation. Statistical analyses were performed using GraphPad Prism (GraphPad Software, La Jolla, CA). Normally distributed data were expressed as mean  $\pm$  standard deviation and skewed data were expressed as median with interquartile range. Normality was determined using the Shapiro-Wilk test. Statistical significance was determined with the Wilcoxon signed-rank test.

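### The planned response to an alert is glucagon and no untreated session is specified, so post-dose data cannot establish predictive-alert specificity or prevention of glucose below 60 mg/dl

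*Protocol*

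**What the plan says.** The protocol synopsis (Study design) describes the trial in these words: "This will be a Phase 2a, single-center, open-label, proof-of-concept study". Study duration says it will "involve up to two infusions of G-Pump™ glucagon at a single visit". Under Visit Day 3, a sensor value below 75 mg/dl is the event "triggering an alert to the physician, who will deliver a bolus". A predictive alert or a further sub-75 reading brings, "within 30-120 minutes after the first dose of glucagon, a second dose of glucagon". Study design adds that nothing is automated and that starting a dose rests with the physician.

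Three analyses depend on what an alert means:

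- **Specificity.** Biostatistical Considerations: "Sensor and glucagon delivery request will be collected and evaluated for specificity and response time". No unit, reference standard, time window or rule for treated alerts is given.
- **Prediction.** The SAP (Study endpoints) lists the algorithm's forecasting of impending lows as a secondary outcome.
- **Prevention.** It is a secondary objective in the protocol, and the SAP lists "prevention of severe postprandial hypoglycemia (plasma glucose <60 mg/dL" mg/dL) as a secondary outcome.

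Two sensors are placed at Visit Day 2 to secure availability and calibration. Visit Day 3 is headed "Mixed Meal Testing (</= 3 days following Visit 2"), with no minimum interval. Afterwards, "Sensors will be downloaded for subsequent analysis of appropriateness of alert timing and trigger for glucagon bolus delivery". The text does not say whether the download analysis includes the days before the session.

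**The concern.** Specificity of a predictive alert asks how often the system stays silent when no low is coming. Prevention asks whether a low that was coming did not arrive. Both need to know what glucose would have done without treatment. In this design the alert that poses the question also triggers the treatment that hides the answer. A participant whose glucose would have levelled off at 65 mg/dl unaided would be counted as a prevented case.

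This matters because the SAP describes iterative development. The false-alert rate is what each algorithm revision needs to know, and a prevention result read as a drug effect would carry forward into later work without support.

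**Working it through.** The documents contain no power calculation or numerical specificity target to reproduce. The check sets out what each analysis can observe, then sizes the gap.

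**Step 1: what the session can and cannot show**

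| Question | Data planned | Answerable? |
|---|---|---|
| Was plasma glucose really low when the sensor read <75? | YSI every 10 min, every 5 min once venous glucose is below 90, until the sensor falls below 75; YSI again 5 min after dosing | Yes |
| Did the system alert and time the dose as programmed (protocol primary endpoint)? | Sensor and delivery-request log | Yes |
| Would glucose have gone below 60 without the dose? | Only values after glucagon | No |
| Was a predictive alert unnecessary? | Predictive alerts are named only for the second dose, so glucose before and after them is already under glucagon | No |

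No other planned element fills the last two rows. The clinic monitoring data in Study design were used to build the algorithm, not as a comparator. The SAP's signed-rank test needs pairs, but none are named and no untreated session exists to supply them. Lunch follows 30 minutes after the last glucagon treatment, so later values also reflect food.

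**Step 2: how often an inert drug would look preventive**

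Let q be the share of participants who would stay at or above 60 mg/dl after the alert without glucagon. The documents do not give q, so a range is used. With 5 participants,

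P(at least 3 of 5 look prevented) = Σ(k=3 to 5) C(5,k) q^k (1−q)^(5−k).

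At q = 0.2: 10(0.008)(0.64) + 5(0.0016)(0.8) + 0.00032 = 0.0512 + 0.0064 + 0.0003 = 0.058.

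| q | 0.2 | 0.4 | 0.5 | 0.6 | 0.8 |
|---|---|---|---|---|---|
| Probability | 0.058 | 0.317 | 0.500 | 0.683 | 0.942 |

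The 3-of-5 cut is borrowed only as a convenient count. The protocol applies it to timing, not to prevention.

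**Step 3: what the pre-session trace could add**

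- Maximum wear: 5 × 3 = 15 person-days. With 1 day of wear: 5 × 1 = 5 person-days. No lower limit is stated.
- Assuming 3 to 6 eating occasions a day (not in the documents): 15 × 3 = 45 to 15 × 6 = 90 meal periods at 3 days, or 15 to 30 at 1 day, against 5 test meals.
- Exact (Clopper–Pearson) 95% intervals if observed specificity were 80%: 4/5 gives 28.4% to 99.5%; 12/15 gives 51.9% to 95.7%; 36/45 gives 65.4% to 90.4%. The last two ignore clustering within participant and are therefore too narrow.

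Meal periods are a better unit than hours. Documented fasting hypoglycemia is an exclusion criterion, so overnight and fasting hours are mostly easy negatives and would inflate an hour-based specificity.

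**Step 4: analysis set**

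The protocol analyses only participants given at least one dose; the SAP analyses all enrolled. A session without an alert or a dose is where true negatives lie, and the protocol's set would drop it.

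**The case against.** The strongest reply is that this is an openly uncontrolled proof-of-concept study with no power calculation, and that the protocol's success rule concerns timing as programmed. That stands. A reader might infer that the 3-of-5 conclusion is biased in the system's favour, but a glucose curve that would have turned by itself cannot affect whether the alert and dose timing followed the program.

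Three other strong readings also fail:

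- *Every alert is treated.* Dosing is the physician's decision, at most two infusions are planned, and no dose is described for an alert in the first 30 minutes after the first one. The documents support only that glucagon is the planned response.
- *The session says nothing about specificity.* Frequent YSI sampling before dosing lets the threshold alert be checked against plasma glucose, and the pre-alert stretch is itself untreated.
- *The wear data are discarded.* The sensors are downloaded for alert analysis with no stated window. The accurate statement is that no use of the pre-session portion is specified.

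It can also be objected that the pre-session trace is a weak reference. It has no YSI and no standard meal, the same device would trigger the alert and define the event, acarbose is permitted, and participants may treat their own lows. This stands too. It is why the replay should supplement the session YSI comparison and not replace it.

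**Conclusion.** The point holds in limited form. Post-dose data from this design cannot establish the specificity of predictive alerts or show that glucagon prevented glucose below 60 mg/dl. The protocol's primary endpoint and the accuracy of the <75 mg/dl threshold alert are outside the criticism.

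The size depends on the unknown q. Between q = 0.4 and q = 0.6, an inert drug would appear preventive in at least 3 of 5 participants with probability 0.32 to 0.68. The pre-session trace could add up to 15 person-days for five participants, but 3 days is a ceiling and actual wear may be much shorter. The conclusion assumes that alerts are generally followed by dosing as planned. The usefulness of the replay also assumes that the downloaded trace includes the days before the session.

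**What to change.** In the SAP:

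1. Define specificity: unit, reference standard, window and handling of treated alerts. Assess threshold-alert accuracy against session YSI values up to dosing. Include sessions in which no dose was given, and reconcile the two documents' analysis sets for this purpose.
2. As a descriptive supplement, replay the algorithm version used in each participant's session on that participant's Visit 2 to Visit 3 trace. Report alerts per day, the fraction followed by sensor glucose below 60 within a pre-stated horizon, the false-alert rate and the lead time. Separate post-meal from fasting periods where meals can be identified, flag self-treated episodes, and acknowledge clustering within participant.
3. Report the session outcome as occurrence of plasma glucose below 60 after dosing, and state that without an untreated meal it is not attributed to glucagon.

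The cost is analysis time and wording. No extra participants, visits or procedures are needed. The replay will lack a YSI reference and a standard meal and may rest on short wear, and the prevention conclusion becomes more modest. Items 1 and 3 are worth making even if the trace proves too short to use.

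### Repeated-measures ANOVA is planned for post-meal hormone profiles whose sampling ends at each participant's own alert, with no rule for the incomplete profiles that result

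*Protocol*

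**What the plan says.** **Analysis.** The protocol synopsis, Biostatistical Considerations, states that the hormone profiles will be "analyzed with commercially available analytical methods and examined using repeated-measures ANOVA". It gives no time window, clock, model terms or rule for missing samples. Its analysis set is subjects who received at least one glucagon dose.

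**Meal-clock sampling.** Visit Day 3 of the synopsis schedules "hormonal profiles at 10, 20, 30, 60, 90, 120, 150, and 180 minutes" after the liquid meal. It then adds: "This blood sampling series will conclude once sensor glucose levels fall to <75 mg/dl". A parenthesis directly after this points to later sample times once the clock is reset at glucagon delivery.

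**Post-dose sampling.** At the bolus, "Time will be reset to 0 at the time of glucagon delivery". From there, "Plasma glucose will be measured (YSI) at 5, 10, 20, 30, 45, 60, 90, and 120 minutes after glucagon administration", and "glucagon levels will be analyzed concurrently to determine magnitude of increase above baseline". No insulin or incretin times are listed on this second clock. A second dose is possible 30 to 120 minutes after the first, and lunch is given 30 minutes after the last dose.

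**SAP.** The Statistics paragraph mentions neither hormones, repeated-measures ANOVA nor missing data. It says only: "Statistical significance was determined with the Wilcoxon signed-rank test". Its Analysis Population paragraph includes all enrolled participants: seven people, two of whom enrolled twice.

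**The concern.** Classical repeated-measures ANOVA needs each participant measured at every time in the model. Here the sampling rule ends the series at a time that differs by participant and depends on that participant's glucose course. The event that ends the series is also, in general, the event that leads to dosing and so to entry into the protocol's analysis set. The stated sampling and the stated analysis therefore do not fit together.

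Two things can go wrong. If software deletes incomplete rows, participants with earlier alerts vanish from the analysis. If means are taken over whoever is left at each time, the late part of the curve describes only participants who had not yet alerted, and a change over time may partly be a change in who is being measured. The protocol assays insulin and incretins to confirm that the meal response looks typical, and the late times are where such selection would act.

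**Working it through.** There is no planned figure to reproduce: neither document gives a power, alpha or precision calculation for the hormone analysis.

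**1. Times left after an alert (exact, from the protocol's grid).** Counting scheduled times at or before the alert, out of 10, 20, 30, 60, 90, 120, 150 and 180:

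- alert at 90 min: 5 of 8
- alert at 120 min: 6 of 8
- alert at 150 min: 7 of 8

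Only an alert at or after 180 min leaves a full profile.

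**2. Expected complete profiles among 5 (assumed alert times).** The cohort size of 5 is the protocol's. The documents give no times from meal to alert, so I assume a lognormal alert time with median m and log-SD s. Then p = 1 − Φ[ln(180/m)/s], and the expected number complete is 5p.

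| Assumed median m (min) | p, s = 0.20 | p, s = 0.35 | Expected complete of 5 |
|---|---|---|---|
| 90 | 0.00 | 0.02 | 0.0 to 0.1 |
| 120 | 0.02 | 0.12 | 0.1 to 0.6 |
| 150 | 0.18 | 0.30 | 0.9 to 1.5 |
| 180 | 0.50 | 0.50 | 2.5 |
| 210 | 0.78 | 0.67 | 3.4 to 3.9 |

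For example, with m = 120 and s = 0.35: ln(1.5)/0.35 = 0.405/0.35 = 1.16, p = 0.12, and 5p = 0.6. Even in the last row, 5 − 3.9 = 1.1 to 5 − 3.4 = 1.6 profiles are expected to be incomplete.

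**3. Possible shift in late means (assumed alert times and correlation).** Suppose hormone level has correlation ρ with an earlier alert, and alert times are Normal(120, 30). Those still sampled at time t then average ρ × φ(z)/[1 − Φ(z)] SD too low, with z = (t − 120)/30. At ρ = 0.5:

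- t = 120: z = 0, 0.5 × 0.399/0.500 = 0.5 × 0.80 = 0.40 SD
- t = 150: z = 1, 0.5 × 0.242/0.159 = 0.5 × 1.53 = 0.76 SD

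At ρ = 0 the shift is zero. Simulation with a lognormal alert time (m = 120, s = 0.35) gave 0.24 SD at 120 min and 0.50 SD at 180 min for ρ = 0.3, and 0.48 and 0.99 SD for ρ = 0.6.

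**4. Post-dose glucagon.** The reset clock has 8 fixed times, 5 to 120 min. A second dose at its earliest, 30 min, leaves 4 of 8 times uninterrupted (5, 10, 20, 30). After a single dose, the other four (45, 60, 90, 120) come after lunch has been provided.

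**The case against.** Several points on the other side stand.

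- **The count of complete profiles is unknown.** A reader might infer that almost nobody will have the full grid, or that the ANOVA would delete nearly everyone. The documents report no alert times. Those statements hold if the median alert is at about 120 min or earlier, and fail at about 180 min or later.
- **Glucagon continues.** A reader might infer that all hormone sampling stops at the alert. It does not: glucagon moves to a fixed 5-120 min grid, where a repeated-measures analysis is workable unless a second dose or lunch disturbs it. The truncation applies to insulin, incretins and pre-dose glucagon.
- **Bias is conditional.** It is plausible that larger insulin or incretin responses bring earlier alerts, but neither document says so or quantifies it.
- **Dose pooling is not specified.** The protocol allows 150 or 300 µg and possibly a second dose, but it does not say that these will be pooled. That is a gap, not a stated error.
- **The stopping sentence could be narrower.** It follows the sentence on 5-minute glucose sampling and might refer only to that. The parenthesis about sample timing after the reset, and the absence of insulin or incretin times after dosing, favour the wider reading.
- **The current text would permit a sound analysis**, such as one limited to common pre-alert times. It does not ask for one, however, and the SAP does not supply it.

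What remains is that, for any participant dosed on an alert before 180 min, the stated method and the stated sampling do not fit, and no rule resolves this.

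**Conclusion.** The point holds on the natural reading of the stopping sentence. Each analysed participant dosed on an alert before 180 min has an incomplete meal-clock profile, and the named method either drops that participant or compares different participants across times. The loss per participant is exact (1 to 3 of 8 times for alerts at 150 down to 90 min). The number of participants affected, and any shift in late means, rest on assumed alert times and an assumed correlation, and should be read only as ranges.

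The consequence is limited. Hormones are not among the protocol's primary or secondary objectives or the SAP's endpoints, and the 3-of-5 success rule does not use them. This is worth correcting, but it does not threaten the trial's main conclusions.

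**What to change.** Put the same paragraph in the protocol's Biostatistical Considerations and in the SAP:

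1. State that the stopping sentence ends hormone as well as glucose sampling on the meal clock, if that is what is meant.
2. Limit the repeated-measures comparison to baseline and the meal times that every analysed participant reached before the alert. Fix that rule, not a particular cut-off, in advance.
3. Show later meal times descriptively, with the number sampled at each time and individual curves, or fit a mixed model to all available samples. With so few profiles, treat the model as supportive and state its assumption about why later samples are absent.
4. Analyse post-dose glucagon separately on the reset clock, by dose received and cut at any second dose. Mark the samples taken after lunch.
5. Treat the two repeat enrolments as clustered within person, not as independent profiles.
6. Reconcile the protocol's dosed-only analysis set with the SAP's all-enrolled set for these data.

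The cost is about one paragraph of wording and no new data. The downside is that late meal times get no formal test; the sampling rule does not support one unless alerts come late.
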